10.3. Tertiary endpoints (Amended: 11 July 2019)

- Evaluation of CMI parameters in terms of frequencies of:
 - Antigen-specific CD4+/CD8+ T-cells identified as producing at least two markers among CD40L, IL-2, TNF- α and IFN- γ upon *in vitro* stimulation at Days 1, 29 **and** 85.
 - B-memory cells reactive with the challenge antigen(s) at Days 1, 8, 29, 64 **and** 85.
 - Plasmablasts reactive with the challenge antigens at Days 1, 8 **and** 64.
- Levels of HI antibody to chimeric vaccine strains **cH5/1N1 and cH8/1N1**:
The following aggregate variables will be calculated with 95% CI:
 - Seropositivity rates and GMTs at Days 1, 29 **and** 85.
 - Seroprotection rate (SPR) at each timepoint listed above.
 - Seroconversion rate (SCR) at Days 29 **and** 85.
 - MGI from Day 1 to each subsequent timepoint listed above.
- Assessment of the *in vivo* protective effect of the anti-stalk antibodies when transferring Day 1 **and** Day 85 pooled serum from all evaluable subjects of each vaccine groups to mice that will be subsequently challenged with cH6/1N5* or with H1N1 contained in the IIV4, using the following endpoints [refer to [APPENDIX D](#)]:

- Survival over 14 days post-challenge (day of death/euthanasia for weight loss > 25% baseline body weight) in groups of 35 mice**/serum pool/vaccine group/timepoint.
- Weight loss (change from baseline over 14 days post-challenge) in groups of 35 mice**/serum pool/vaccine group/timepoint.
- Lung virus titer in TCID₅₀/mg (\log_{10} fold change [Day 1 minus Day 85]), within challenge group.
- Pre- and post-transfer titer of human IgG to cH6/1N5* by ELISA or HI.
- Pre- and post-transfer titer of human IgG to H1N1 by ELISA or HI.
- Pre- and post-transfer titer of human IgG to recombinant HA protein by ELISA.

*Or an alternative challenge virus with similar attributes but more fit for purpose.

**If sufficient serum volumes are not available, and depending on the challenge virus pathogenicity, the number of mice can be reduced to as low as 10 mice per timepoint and virus challenge.

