 - 1A: Survival over 14 days post-challenge (day of death or euthanasia for weight loss > 25% baseline body weight) in groups of 10 to 35 mice/human-group/timepoint (number of mice = most likely 25, to be decided upon the pathogenicity of the challenge virus in mice; the exact sample size will be specified in an annex statistical report).
 - 1B: Weight loss (change from baseline over 14 days post-challenge) in groups of 10 to 35 mice/human-group/timepoint.
 - 1C: Lung virus titer in TCID₅₀/mg on Day 3 and/or Day 6 post-challenge in subset of 5 mice for each timepoint. This assessment will be performed at Day 3 or Day 6 post-challenge, or both, depending on anticipated additional supportive pre-clinical data.Comparisons between FLU D-SUIV-ADJ-001 study groups and/or timepoints (Day 1 **and** Day 85) will be investigated.
2. The association between pre- or post-transfer human IgG binding antibody titers to the challenge viruses and the lung virus titer at Day 3 and/or Day 6 and the post-challenge outcome will be explored.
 - 2A: Measure of the pre- and post-transfer geometric mean human IgG binding antibody specific to cH6/1Nx virus, H1N1 virus or recombinant HA proteins in blood collected from mice receiving either one of the serum pools (Day 1 **and** Day 85).
 - 2B: Descriptive analyses will be conducted to detect possible associations between the antibody titers as measured in 2A and post-challenge endpoints.
 - a. Proportion of survival over 14 days post-challenge,
 - b. Weight loss,
 - c. Geometric mean lung virus titer.

Protocol endpoints (**Amended: 11 July 2019**):

Objective	Endpoint
1A	Survival over 14 days post-challenge (day of death or euthanasia for weight loss >25% baseline body weight) in groups of 10 to 35 mice*/serum pool/timepoint
1B	Weight loss (change from baseline over 14 days post-challenge) in groups of 10 to 35 mice*/serum pool/timepoint
1C	Lung virus titer in TCID ₅₀ /mg (log ₁₀ fold change (D1 - D85)), within challenge group
2A	Pre- or post-transfer of human IgG binding antibody titers to cH6/1Nx virus by ELISA or HI, Pre- or post-transfer of human IgG binding antibody titers to H1N1 virus by ELISA or HI Pre- or post-transfer of human IgG binding antibody titers to recombinant HA proteins by ELISA

*If sufficient serum volumes are not available and depending on the challenge virus pathogenicity, the number of mice can be reduced to as low as 10 mice per timepoint and virus challenge

Methods

Viruses:

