Challenge virus	Surface glycoprotein attributes	Virus-specific protection mediated by
cH6/1Nx (or an alternative challenge virus with similar attributes but more fit for purpose)	
 Exotic HA head domain not matched to vaccine strains HA stalk domain from H1-representative of all group A1 influenza stalk, matched to vaccine strains Exotic neuraminidase not matched to vaccine strain 	HA stalk antibody responses
H1N1 virus (most likely strain contained in the IIV4 control)	
 HA head domain, matched to circulating strain HA stalk domain matched to vaccine strain Neuraminidase matched to vaccine strain 	HA (stalk and head) and NA antibody responses

Both viruses will be pre-assessed for mouse lethality in LD₅₀ experiments (in the presence of control adult human serum pools). The volume and route of inoculation will be 0.05 mL intra-nasal/intra-tracheal administered to anesthetized mice.

Human serum pools:

Serum pools will be created using serum samples from all evaluable subjects to constitute an aliquot of an equal volume across the groups and the timepoints Day 1 **and** Day 85 from the FLU D-SUIV-ADJ-001 cohort. (**Amended: 11 July 2019**)

Passive transfer experimental method:

- Twenty to 35 mice per timepoint per virus challenge will be transferred with a standard amount of undiluted human pooled serum (volume to be determined, within the range 150-250 µL). The exact sample size by challenge study will be specified in an annex statistical report. Also, most likely all the human group serums will be tested but some groups might be excluded depending on the results obtained, as the clinical trial progresses and in accordance with the animal ethical 3R's principles. Pre-transfer pooled serum human IgG titers against HA proteins or influenza virus will be evaluated by ELISA as previously mentioned.
- Two hours post serum transfer, the mice will be sedated and:
 - Blood will be collected for determination of post-transfer human IgG titers against HA proteins or influenza viruses by ELISA.
 - Then challenged with 10 x LD₅₀ delivered by the IN/IT route.
- Mice will be monitored daily for 14 days for weight-loss and will be euthanized if they lose > 25% of their initial body weight or if any human endpoints defined in the ethical protocol are met.

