- On Day 3 and/or Day 6 post-infection, 5 mice per timepoint/virus will be euthanized to assess viral lung titers. This will occur at Day 3 or Day 6 post-challenge, or both, depending on anticipated additional supportive pre-clinical data. Upon results, lung histopathology may be performed at selected timepoints on relevant groups.
- Weighing of the mice and lungs processing will be performed in an open fashion. Viral plaques will be counted by a blinded technician.
- Lung suspensions will be made by homogenization in PBS and frozen at -80°C for later plaque assay using a standard method.

Statistical analytical plan:

Statistical analysis will be performed to evaluate the improved survival after challenge of any vaccine groups (mice receiving human pooled serum from chimeric HA- approach groups) compared to control group (mice receiving human pooled serum from IIV4 group), measured at each timepoint. Additional analysis might be added to the study to detect potential association between post-transfer titers and survival, post-transfer titers and weight loss or between lung-titers at Day 3 or Day 6 and survival.

The analyses and reporting of those data will be handled by the pre-clinical team according to their processes. No data will be incorporated in the clinical study report, but presented as an appendix.

Ethical statement:

The study protocol will be ethically reviewed and approved by the appropriate ethical committee and the study will be carried out in accordance with national and international directives and the GSK Biologicals' policy on the care, welfare and treatment of animals.

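### Passive-transfer mice are weighed unblinded although weight loss decides survival, and with one serum pool per group and timepoint the survival comparisons speak only for the pools tested

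*Protocol*

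**What the plan says.** Section 10.3 makes the mouse experiment a tertiary endpoint, transferring Day 1 and Day 85 "pooled serum from all evaluable subjects of each vaccine groups to mice". Appendix D (Human serum pools) repeats the pooling: "Serum pools will be created using serum samples from all evaluable subjects to constitute an aliquot of an equal volume across the groups". Neither place describes individual sera or replicate pools.

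Mouse numbers are left open. Section 10.3 gives 35 per pool, reducible to 10. The Appendix D objectives give 10 to 35, with "number of mice = most likely 25, to be decided upon the pathogenicity of the challenge virus in mice", and add that "the exact sample size will be specified in an annex statistical report".

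Endpoint 1A is "Survival over 14 days post-challenge (day of death or euthanasia for weight loss > 25% baseline body weight"). Endpoint 1B is weight loss over the same 14 days. On blinding, the experimental method says "Weighing of the mice and lungs processing will be performed in an open fashion" and assigns only the viral plaque count to a blinded technician.

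The analysis paragraph of Appendix D says "Statistical analysis will be performed to evaluate the improved survival after challenge of any vaccine groups" against mice given the IIV4 pool, at each timepoint. It leaves analysis and reporting to the pre-clinical team.

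Section 5.3, on the method of blinding, keeps those who evaluate any study endpoint unaware of what was administered, and has the testing laboratory work on coded samples.

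**The concern.** There are two separate issues.

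**Blinding.** The weight reading feeds both endpoint 1B and, through the 25% rule, the time of death in endpoint 1A. If the person at the cage knows which pool the animal received, then handling, re-weighing of borderline readings and the timing of euthanasia can all be influenced. Any such influence would act on the contrast of interest.

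**Replication.** The 10 to 35 mice given one pool replicate that pool, not the vaccinees behind it. Variation between mice says how reliably two particular pools differ. It says nothing about how much those pools would have differed had other subjects been randomised to the same vaccines. The tertiary objective concerns antibodies induced by vaccination, so a reader will want to generalise from pools to vaccine groups, and the design gives no error term for that step.

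**Working it through.** **Blinding, passages side by side.**

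1. Section 10.3 lists mouse survival and weight loss among the study's tertiary endpoints.
2. Section 5.3 says evaluators of any study endpoint are unaware of the product.
3. Appendix D has weighing done openly and blinds only the plaque count.
4. Appendix D counts euthanasia for more than 25% weight loss as a survival event. It also allows euthanasia on other endpoints of the ethical protocol, with no stated blinding.

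Points 2 and 3 do not fit together for the read-out that determines 1A and 1B. The protocol contains no figure from which a bias could be computed, so none is given.

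**Replication, inputs.** The protocol gives no power, alpha or sample-size derivation for the mice, so there is no figure to reproduce. The inputs used are:

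- subjects per pool: about 43 evaluable per group (Section 10.4.1);
- between-subject SD of log10 anti-stalk titre: 0.45 and 0.50 (Section 10.4.1; 0.43 was observed in an earlier study with a different ELISA).

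As a check that the SDs are read correctly, the two-sample power formula with 129 per pooled group, a 1.5-fold margin and alpha 0.0554 gives 0.799 at 2.14-fold with SD 0.45 and 0.802 at 2.23-fold with SD 0.50. Table 30 has 0.800 for both.

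**Chance difference between two pools from identical vaccine groups.**

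Geometric scale: SD of one pool = SD/√43; 95% limit of the fold ratio = 10^(1.96 × SD × √(2/43)).

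- SD 0.45: pool SD 0.0686; 1.96 × 0.0686 × √2 = 0.190; 10^0.190 = **1.55-fold**.
- SD 0.50: pool SD 0.0762; 1.96 × 0.0762 × √2 = 0.211; 10^0.211 = **1.63-fold**.

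Mixing equal volumes averages titres arithmetically, which gives high responders more weight. Simulating 43 log-normal titres per pool gives pool SDs of 0.0889 and 0.1041 log10, hence limits of **1.76-fold** (SD 0.45) and **1.94-fold** (SD 0.50).

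With one pool per group and timepoint, the between-pool error has 1 − 1 = 0 degrees of freedom in each group. It cannot be estimated from the mice under any model.

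**Does this reach the survival comparison?** Only through the relation between titre and survival, which the protocol does not state. I simulated two identical vaccine groups with SD 0.45, 50% survival, 25 or 35 mice per pool and an assumed mouse-level two-proportion test at 5%:

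| Assumed rise in survival odds per titre doubling | Rejections |
|---|---|
| none | 4–6% |
| 1.8-fold | 7–9% |
| 3.3-fold | 16% |
| 6.1-fold | 25–27% |

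The slope, test, alpha and survival level are all assumptions. The table shows that the answer depends on the slope; it does not estimate this experiment's error rate.

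**The case against.** The strongest defence is that Appendix D commits to no faulty test. It names no unit of analysis, alpha or p-value, leaves mouse numbers to an annex and analysis to the pre-clinical team, and describes the arms of the comparison as mice receiving pooled serum. Mouse-level error is valid for comparing two specific pools. This stands. A reader might infer that the protocol plans mouse-level p-values with a false-positive rate of 11% to 35%. Those figures need within-pool correlations (0.02 to 0.10) and a 5% test that appear nowhere in the document, so they should not be attached to it.

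A reader might also infer that one pool per group amounts to a single observation with nothing to say about the group. That is too strong. Each pool averages about 43 subjects. Individual ELISA and MN titres are reported with confidence intervals (Sections 10.1 and 10.9.1.1), and pre- and post-transfer pool titres are measured and related descriptively to outcome (Appendix D, objectives 2A and 2B), so a chance titre difference between pools would be visible. Day 1 versus Day 85 contrasts within a group are less affected, since largely the same subjects should contribute.

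On weighing, the trigger is a numerical threshold on a scale, which limits the room for bias, and Section 5.3 was written mainly with clinical evaluation in mind. Both points reduce the concern. Neither explains why one mouse read-out is blinded and the one that decides survival is not.

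What the defence cannot remove is that a later analysis plan cannot recover between-subject error once the sera are in one pool.

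**Conclusion.** The point holds in a limited form. Open weighing of animals whose weight loss determines survival is an avoidable weakness and does not fit Section 5.3; its effect is of unknown size. Separately, the comparison with IIV4 supports statements about the pools tested and not, inferentially, about vaccine groups, because chance alone could separate pools from identical groups by about 1.55- to 1.63-fold in titre (geometric, 95% limit), or 1.76- to 1.94-fold with arithmetic mixing. These limits assume log-normal titres, about 43 contributors per pool and the protocol's SDs, which come from a different assay. How far such a difference would move mouse survival depends on a slope the protocol does not give.

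The consequence is small. The experiment is tertiary, described as exploratory and reported only as an appendix, no primary or secondary endpoint rests on it, and the sponsor has already decided not to pursue the vaccine.

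**What to change.** 1. In Appendix D, replace open weighing with coded serum vials and cages, so that staff who weigh the mice and decide on euthanasia do not know vaccine group or timepoint. Someone outside the cage-side team holds the key. The cost is minor coding work, with no extra animals or serum.

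2. In the analysis paragraph of Appendix D, state that survival comparisons refer to the pools tested. Report them descriptively next to the measured pre- and post-transfer pool titres, without inferential claims about vaccine groups. This costs a sentence and applies equally if the pools have already been made.

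3. Optionally, where mouse numbers allow, use several independent sub-pools per group and timepoint, with sub-pool as the unit or a random effect. Five sub-pools would mean 5 to 7 mice each at 25 to 35 mice, but only 2 each at the permitted minimum of 10. They would also raise the number of pools to prepare and titrate from 10 × 2 = 20 to 10 × 2 × 5 = 100. That is a real trade-off, so it is not a condition of the first two changes.

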APPENDIX E AMENDMENTS AND ADMINISTRATIVE CHANGES TO THE PROTOCOL

GlaxoSmithKline Biologicals SA Vaccines R&D Protocol Amendment 1	
eTrack study number and Abbreviated Title	207543 (FLU D-SUIV-ADJ-001)
IND number	17602
EudraCT number	2017-001584-20
Amendment number:	Amendment 1
Amendment date:	24 October 2017
Co-ordinating author:	PPD, Scientific Writer (XPE Pharma & Science for GSK Biologicals)
Rationale/background for changes: This protocol is amended for the following reasons:	

 • To ensure that only healthy subjects with no risk factors for severe influenza-related complications can be enrolled, an additional exclusion criterion has been added: 
 – Any condition that puts the subject at risk for serious influenza-related complications, as identified by the Advisory Committee on Immunization Practices. • To account for an higher rate of non-evaluable subjects, the sample size has been increased by 20 subjects. • The possibility to use a qualitative assay for the RSV-PCR assay has been added. • To add the possibility to assess the lung titers in mice in the passive transfer experiment at Day 3 or at Day 6 post-challenge, or both, depending on anticipated additional supportive pre-clinical data; and to clarify that the pool of serum will be obtained using serum samples from evaluable subjects. • To update the list of potential Immune-Mediated Diseases (pIMDs) to be aligned with the new version of the Medical Dictionary for Regulatory Activities. In addition, gout was added as the monitoring plan for this event (now considered a pIMD) became a commitment for the Company. 	

- To clarify that the vaccines/products must be brought to room temperature before reconstitution/preparation instead of before use.
- To correct values in the Table 27 presenting 2-sided exact 95% confidence intervals for the true immunological response rate at different possible observed response rates.
- To include the IND number which was assigned after protocol finalization.

In addition, minor corrections/updates have been made and the list of contributing authors has been updated.

Amended text has been included in *bold italics* and deleted text in ~~strikethrough~~ in the following sections:

Cover page

The symbol TM has been deleted and the trademark has been put in italics:

Other study vaccines/products	• GSK Biologicals' quadrivalent split virion influenza vaccine Fluarix QuadrivalentTM
--	---

The following change has also been implemented on the Sponsor and Investigator Approval pages:

Investigational New Drug (IND) number	To be provided 17602
--	-----------------------------

Contributing authors (continued)	
 • [...] • PPD ██████████, PPD ██████████, Global Patent representatives • PPD ██████████, PPD ██████████, Pre-clinical representatives
---	---

**Copyright 2017 the GlaxoSmithKline group of companies or its licensor. All rights reserved.
Unauthorized copying or use of this information is prohibited.**

Glossary of terms

Protocol amendment:

The International Conference on Harmonisation (ICH) defines a protocol amendment as: “A written description of (a) change(s) to or formal clarification of a protocol”. GSK Biologicals further details this to include a change to an approved protocol that affects the safety of subjects, scope of the investigation, study design, or scientific integrity of the study.

Trademarks

The symbols TM have been deleted and the trademarks have been put in italics:

[figure not shown]
* Areprix TM
Fluarix TM
Mosquirix TM
** Pandemrix TM

Section 1.2.2 Rationale for the study design (+ in synopsis)

Approximately 450 **470** subjects 18-39 years of age will be equally randomized in 10 different treatment groups to receive [...]

Section 3 Study design overview (+ in synopsis)**Figure 1: Study design overview**

The number of subjects has been updated (at the top of the figure):

**Table 1: Study groups and epochs foreseen in the study**

Study Groups	Number of subjects	Age (Min - Max)	Epochs	
			Epoch 002	Epoch 003
cH8/P/cH5-AS03	45 47	18 years – 39 years	x	x
cH5/P/cH8-AS03	45 47	18 years – 39 years	x	x
cH8/5/11-AS03	45 47	18 years – 39 years	x	x
cH8/P/cH5-AS01	45 47	18 years – 39 years	x	x
cH5/P/cH8-AS01	45 47	18 years – 39 years	x	x
cH8/5/11-AS01	45 47	18 years – 39 years	x	x
cH8/P/cH5	45 47	18 years – 39 years	x	x
cH5/P/cH8	45 47	18 years – 39 years	x	x
cH8/5/11	45 47	18 years – 39 years	x	x
IIV4	45 47	18 years – 39 years	x	x

- **Sampling schedule:**
 - [...]
 - Blood samples for cell-mediated immunity (CMI) assessment will be drawn from a sub-cohort of ~50% of ~225 subjects at Days 1 (Visit 1), [...]
- **Enrolment:** the study will follow a staggered enrolment with 2 steps; the first being Phase I (N = ~80) and the second being Phase II (N = ~370 **390**):

Section 4.1 Number of subjects/centers (+ in synopsis)

This study will be conducted in multiple centers. A total of **450 470** subjects (45 47/group) are planned to be enrolled in this study, in order to have 430 evaluable subjects for the primary immunogenicity endpoints. [...]

Table 4 Sub-cohort

Sub-cohort name	Description	Estimated number of subjects
Cell-mediated immunity (CMI) testing	Additional blood sample (~40 mL) to be taken at Visits 1, 2, 3, 5, 6, 8, 9, 10 and 12 for CMI testing. This will be done at pre-specified sites with adequate material for such sampling procedure.	Approximately 225 (~50% of the enrolled subjects) The sub-cohort will consist of the first Phase II subjects enrolled in pre-specified sites.

Section 4.3 Exclusion criteria for enrolment

- Chronic administration (defined as more than 14 days in total) of immunosuppressants [...], or equivalent. ~~Inhaled and~~ Topical steroids are allowed.
- [...]
- *Any condition that puts the subject at risk for serious influenza-related complications, as identified by the Advisory Committee on Immunization Practices [Grohskopf, 2017] (note that only criteria applicable for the study population are listed below):*
 - *Chronic pulmonary (including asthma), cardiovascular (except isolated hypertension), renal, hepatic, neurologic, hematologic or metabolic disorders (including diabetes mellitus);*
 - *Persons who are immunocompromised due to any cause (including immunosuppression caused by medications or by HIV infection);*
 - *Adolescents (through 18 years) who are receiving aspirin- or salicylate-containing medications and who might be at risk for experiencing Reye syndrome after influenza virus infection;*
 - *Residents of nursing homes and other long-term care facilities;*
 - *American Indians/Alaska Natives; and*
 - *Persons who are extremely obese (Body Mass Index ≥ 40).*

Section 5.2.2.2.1 Study group and treatment number allocation

The target will be to enroll ~**450 470** eligible subjects who will be randomly assigned to 10 study groups in a (1:1:1:1:1:1:1:1:1:1) ratio (~45 47 subjects in each group).

Section 5.7.3 Laboratory assay**Table 12 Molecular Biology (PCR tests)**

Component	Kit/ Manufacturer	Method	Unit	Laboratory
Nasal swab samples				
[...]	[...]	[...]	[...]	GSK Biologicals* or designated laboratory
RSV A virus (RSV A) RSV B virus (RSV B)	In-house	Quantitative or qualitative RT-PCR	Copies/mL or pos/neg	

Pos/neg = positive/negative

*GSK Biologicals laboratory refers to the CLS in Rixensart, Belgium; Wavre, Belgium.

Section 5.7.4.1 Immunological read-outs**Table 13 Immunological read-outs for humoral immunity and cell-mediated immunity**

Type of contact and timepoint	Blood sampling timepoint	Sub-cohort Name	No. subjects	Component	Components priority rank
Humoral immunity					
Visit 1 (Day 1) [...]	PRE [...]	All subjects	~450 ~470	Anti-H1 HA stalk ELISA [...]	P P [D]
Visit 1 (Day 1) [...]	PRE [...]	All subjects	~450 ~470	Anti-H1 HA stalk MN assay [...]	P P [D]
Visit 1 (Day 1) [...]	PRE [...]	All subjects	~450 ~470	HI with IIV4 H1N1 strain from 2017/2018 season	P P
Visit 8 (Month 14) [...]	M14 [...]	All subjects	~450 ~470	HI with IIV4 H1N1 strain from 2018/2019 season [...]	P P D...

Section 6.3 Dosage and administration of study vaccines/products

[...]

All vials of vaccines/products should be kept at room temperature for at least 15 *a few* minutes prior to use **reconstitution/preparation**. All vaccines/products must be administered within one hour of reconstitution/preparation *after being taken out of the fridge*.

Section 8.1.6.1 Potential immune-mediated diseases**Table 20 List of potential immune-mediated diseases**

Neuro-inflammatory disorders	Musculoskeletal disorders	Skin disorders

 ● [...] ● Myasthenia gravis, including Lambert-Eaton myasthenic syndrome ● Immune-mediated peripheral neuropathies and plexopathies, (including chronic inflammatory demyelinating polyneuropathy, multifocal motor neuropathy and polyneuropathies associated with monoclonal gammopathy). ● Demyelinating peripheral neuropathies including: 
 – Chronic inflammatory demyelinating polyneuropathy – Multifocal motor neuropathy – Polyneuropathies associated with monoclonal gammopathy ● Narcolepsy 	
 ● [...] ● Systemic scleroderma (systemic sclerosis), including: 
 – Diffuse systemic form scleroderma – CREST syndrome ● [...] ● Rheumatoid arthritis, and associated conditions including: 
 – Juvenile chronic idiopathic arthritis – Still's disease ● Polymyalgia rheumatica ● Spondyloarthritis ● Spondyloarthropathies, including: 
 – [...] – Psoriatic arthropathy arthritis – Enteropathic arthritis ● [...] ● Gout 	
 ● [...] ● Autoimmune bullous skin diseases (including pemphigus, pemphigoid and dermatitis herpetiformis) ● Alopecia areata ● [...]
Vasculitides 
 ● Large vessels vasculitis including: 
 – Giant cell arteritis (temporal arteritis) such as – Takayasu's arteritis and temporal arteritis. ● Medium sized and/or small vessels vasculitis including: 
 – [...] – Wegener's granulomatosis (granulomatosis with polyangiitis) – Churg–Strauss syndrome (allergic granulomatous angiitis or eosinophilic granulomatosis with polyangiitis) – Buerger's disease (thromboangiitis obliterans), – Necrotizing vasculitis (cutaneous or systemic), ● Anti-neutrophil cytoplasmic antibody (ANCA) positive vasculitis (type unspecified), ● Henoch-Schonlein purpura (IgA vasculitis), ● [...] 	Blood disorders 
 ● Autoimmune hemolytic anemia ● [...] 	Others 
 ● Autoimmune glomerulonephritis, including: 
 – [...] – Tubulo-intestinal nephritis and uveitis syndrome ● Ocular autoimmune diseases, including: 
 – Autoimmune uveitis – Autoimmune retinopathy retinitis ● Autoimmune myocarditis/cardiomyopathy ● [...] ● Alopecia areata ● [...]

Liver disorders	Gastrointestinal disorders	Endocrine disorders

 Autoimmune hepatitis [...] 	
 Inflammatory Bowel disease, including: 
 Crohn's disease [...] 	
 Autoimmune thyroiditis (including Hashimoto thyroiditis) [...]

Section 8.8.1 Holding rules

[...]

Figure 2 gives the probability of not meeting each holding rule 1 and 2 for the 45 subjects in an investigational group. *This evaluation was performed for the sample size of the initial protocol (i.e. 450 subjects, 45/group) and it was not repeated at the time of the protocol amendment 1 because of the small difference in the number of subjects per group (now 470 subjects in total, 47/group).*

Section 10.3 Tertiary endpoints (+ in synopsis)

- Assessment of the *in vivo* protective effect of the anti-stalk antibodies when transferring Day 1, Day 85, Month 14 and Month 26 pooled serum from all *evaluable* subjects of each vaccine groups [...]

Section 10.4.1 Descriptive objectives

[...]

At the time of the protocol amendment 1, it was decided to increase the sample size from 450 to 470 subjects to take into account a larger rate of non-evaluable subjects than anticipated. The power computations from the initial protocol relative to safety endpoints were not modified because of the small sample size increase (about 2 subjects per group, from 45 to 47). The immunogenicity endpoints evaluation will be done primarily on the Per-Protocol set, which is not deemed to increase (about 43 subjects per group).

[...]

Table 27 presents the 95% CIs for different possible rates of immunological response within each group. A rate of unevaluable subjects of 2/45 (4%) has *initially* been considered for the immune response post-primary vaccination. *As from protocol amendment 1, a rate of non-evaluable subjects of 4/47 (9%) has been considered for the immune response post-primary vaccination.*

Table 27 Two-sided exact 95% confidence intervals for the true immunological response rate at different possible observed response rates (43 evaluable subjects)

Observed number of responses	Observed response proportion	95% exact confidence interval	
		Lower limit	Upper limit
25	0.581	0.421	0.730
30	0.698	0.547 0.539	0.828
35	0.781 0.814	0.667	0.916
40	0.930	0.809	0.985

